Analysis of the two concurrent vitamin D pregnancy NICHD (n=350) and Thrasher Research Fund (n=157) trials was undertaken to assess the health characteristics and outcomes of this larger, combined group using a common data dictionary (8). As noted above, in the NICHD trial, women were randomized to 400 IU (10 μ g), 2000 IU (50 μg) or 4000 IU (100 μg)/day, stratified by race. In Thrasher trial, participants were randomized to 2000 (50 μ g) or 4000 IU (100 μ g)/day, also stratified by race. All participants received study drugs from the same manufacturing lot. Studies administered identical questionnaires to produce comparable sociodemographic/clinical characteristics. Outcome measures included: (1) maternal baseline and delivery 25(OH)D; (2) neonatal 25(OH)D; (3) comorbidities of pregnancy: gestational diabetes, hypertensive disorders of pregnancy, infection—any, bacterial vaginosis (BV), and preterm birth without preeclampsia. In the combined cohort, there were 110 in the control group, 197 in 2000 IU group, and 189 in the 4000 IU group. The treatment groups differed on the basis of parity (p=0.022); insurance status (Medicaid status more common in the 2000 IU group p=0.006); and education (higher education level in the 400 IU group, p=0.012). No differences were noted between groups in baseline 25(OH)D (p=0.24), but differences between groups were noted in vitamin D status within one month of delivery (p<0.0001) and in cord blood (p=0.0001), with improved status in the 4000-IU group overall. No differences were noted between groups in terms of independent or combined comorbidities of pregnancy. There was a trend where preterm birth without preeclampsia was lower with increasing 25(OH)D concentration (Odds Ratio (OR) 0.83 (Confidence Interval (CI) 0.68-1.01); p=0.057). The risk of combined comorbidities of pregnancy adjusted for race/ethnicity and study was significantly lower with increasing 25(OH)D concentration (Odds Ratio per 10 ng/mL increase in 25(OH)D: 0.84; 95% CI 0.74-0.96; p=0.0095) (8).

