The debate about what constitutes frank deficiency, insufficiency, and sufficiency continues (3, 117). The answer varies depending on the question—is the outcome bone integrity or immune function? There could be a different cut point for each category. Most would agree—including the Institute of Medicine in their most recent statement –that levels below 20 ng/mL (100 nmol/L) represent deficiency in the nonpregnant individual. There is less consensus with respect to pregnancy: based on our recent randomized controlled trial with pregnant women, it is clear that optimization of 1,25(OH)₂D does not occur until total circulating 25(OH)D levels have reached 40 ng/mL (100 nmol/L) (5).

The significance of these trials is that vitamin D status is improved with 4000 IU vitamin D₃ taken daily to achieve: (1) optimization of 1,25(OH)₂D production, and (2) improved cord blood 25(OH)D concentration. Having a higher 25(OH)D concentration was associated with improved health outcomes in both studies, but whether improved vitamin D status is a marker of some other parameter or a direct effect of vitamin D supplementation remains unclear at this time. Studies specifically designed and powered to answer the question of whether or

not vitamin D supplementation leads to improved health outcomes—lower risk of preterm birth, preeclampsia, and infection remain to be done. We can conservatively say that while we do not understand completely the role of $1,25(OH)_2D$ during pregnancy, achieving optimal production can be done safely with 4000 IU vitamin D₃/day, which appears to be the amount of vitamin D that would be conservatively generated by the body with adequate sunlight exposure over the duration of gestation.

D. RESEARCH DESIGN AND METHODS (including data analysis)

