Study Design: This is a randomized, placebo-controlled clinical trial of 450 pregnant women who will be enrolled between 10-14 weeks of gestation and followed until delivery. Following written, informed consent, each mother will be randomized to receive either placebo or 4000 IU/day vitamin D₃ plus the standard prenatal vitamin (containing 400 IU vitamin D₃). She will be followed monthly for a total of nine study visits. If, after 3 months of vitamin D supplementation, a mother is still frankly vitamin D deficient (less than 15 ng/ml), she will receive open label active vitamin D gummies for the remainder of her pregnancy. These visits will include the initial recruitment of mother at 10-14 weeks of pregnancy, monthly study visits, delivery study visit, and 18-month post-partum follow-up visit for mother and child. The primary outcome variable is maternal and neonatal health status as a function of maternal and infant vitamin D status. Secondary outcome variables to be analyzed, as a function of maternal vitamin D status during pregnancy will include: T-lymphocyte profile, immune function indicators, neonatal growth, inflammatory cytokine profile, methylation patterns of DNA of both mother and her neonate,

(1) Subject Selection Criteria and Recruitment: Any mother (18-45 years of age) who presents to her obstetrician or midwife at the Medical University of SC (MUSC), Charleston, SC obstetrical facilities within the first 14 weeks after her last menstrual period (LMP) with confirmation of a singleton pregnancy will be eligible for enrollment in the study. Mothers of diverse ethnic backgrounds (African-American, Asian, Caucasian and Hispanic) will be actively recruited. A database will be generated weekly of undelivered patients for the labor and delivery staff continue to alert the staff of impending admissions.

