(14) Maternal Physical Activity Assessment Questionnaire: Each mother will be asked to complete a Physical Activity Assessment Questionnaire. This questionnaire utilizes a well-established physical activity instrument with known validity and reliability. Because physical activity can affect calcium metabolism and because a woman's activity level may change considerably during her pregnancy, it will be important to reassess maternal activity level throughout the entire period of gestation. Therefore, each mother will complete this questionnaire monthly.

(15) Sunlight Exposure: Two body sites will be scored at each monthly visit with a Smart Probe (measures skin color at 450 nm wavelength) to assess sunlight exposure.

(16) Maternal Physical Examination: As part of MUSC's OB clinic, each mother undergoes a physical examination at scheduled clinic visits, according to standard of care for the OB clinic. Some of these results of the physical exam will be recorded directly on the case report forms.

(17) Maternal Dental Examination: Women with 1 or more natural teeth and not having a health condition that requires antibiotic prophylaxis before periodontal probing are eligible for the periodontal examination.

(a) The commonly used full mouth periodontal examination (FMPE) may be done up to three times during the pregnancy (baseline, 28 weeks and 36 weeks). The FMPE protocol will be used for classification of periodontal disease. The major outcome measure of change in the periodontal measures will be correlated with change in serum circulating 25(OH)D concentration from baseline to 28 and 36 weeks. The FMPE will be done by trained personnel (Registered Dental Hygienist or Dentist) in a dental chair setting. Data are either recorded on paper or direct data entry will be done. The research instruments and questionnaires have all been previously used in the research environment.

(b) Gingival inflammation is measured using a salivary occult blood test (SOBT). The chairside SOBT is done monthly by rinsing the mouth with water and then spitting into a small paper cup. The outcome for SOBT will be analyzed with respect to the periodontal measures, and in particular, the percent of sites with BOP. Trained study personnel will perform the SOBT. Data will be recorded on visit questionnaire. This research instrument has been previously used in the research environment.

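### The main periodontal outcome is given only a correlation with each woman's change in 25(OH)D; no comparison by randomised arm is specified for it

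*Protocol*

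**What the plan says.** Protocol section D, item (17)(a), Maternal Dental Examination, describes a full-mouth periodontal examination that "may be done up to three times during the pregnancy" (baseline, 28 and 36 weeks). It calls change in the periodontal measures the major outcome measure of that examination and states that it "will be correlated with change in serum circulating 25(OH)D concentration from baseline to 28 and 36 weeks". No other analysis of this outcome is given. Items (17)(b) and (17)(c) relate the salivary blood test and the oral Chlamydia test to the periodontal measures (and, for Chlamydia, to birth outcomes), again not to arm.

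A randomised contrast exists. Under Study Design, "each mother will be randomized to receive either placebo or 4000 IU/day", and all women also take a prenatal vitamin containing 400 IU. The same paragraph frames the trial's primary outcome by status: "The primary outcome variable is maternal and neonatal health status as a function of maternal and infant vitamin D status".

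The SAP names no dental or periodontal measure. Its intention-to-treat primary analysis compares maternal 25(OH)D between the two groups. Later it says in general terms that repeated-measures methods will compare outcomes over time between groups, and that the main goal is to study the various outcomes as a function of supplementation.

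**The concern.** Section A of the protocol states a causal hypothesis: correcting deficiency should protect against several disorders, periodontal inflammation among them. Its second objective asks what supplementation prevents. Random assignment answers such a question without confounding, but only if the analysis uses the assignment.

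A woman's change in 25(OH)D is not assigned. The SAP itself lists sunlight, pigmentation, physical activity, diet, health and medication as things to be separated from the effect of supplementation on vitamin D. Protocol item D(21) adds another: women below 15 ng/mL after 3 months go onto open-label vitamin D. Any factor that raises 25(OH)D and also goes with better oral health can produce an association in the beneficial direction, and a reader could take that for a treatment benefit.

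The protocol knows this difficulty. On the earlier trials, section C leaves open "whether improved vitamin D status is a marker of some other parameter or a direct effect of vitamin D supplementation", and section E.4 accepts that those status-based findings were post hoc and show correlation at most. Specifying the correlation in advance removes the post-hoc objection but not the confounding.

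**Working it through.** The documents give no effect size, SD, sample size, alpha or power for a periodontal outcome, so there is no planned figure to reproduce. The check has a textual part and two illustrations.

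**Text.** Periodontal change is linked by name to change in 25(OH)D (protocol D(17)(a)). Intention-to-treat by arm is linked by name to maternal 25(OH)D (SAP, first paragraph). The general between-group wording near the end of the SAP sits among text on vitamin D parameters and names no periodontal measure. The only analysis tied to the periodontal outcome is therefore the correlation.

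**How much of the variation in 25(OH)D change is randomised?**

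- Within-arm SD of change: 13.2 and 12.9 ng/mL in the earlier 2000 vs 4000 IU trial (protocol section C). Pooled: √[(13.2² + 12.9²)/2] = √170.3 = 13.05. That this applies to 400 vs 4400 IU is an assumption.
- Difference between arms, d: not given for 400 vs 4400 IU. Assumed range 10 to 20 ng/mL.
- With 1:1 allocation, share of variance due to arm = (d²/4) / (d²/4 + SD²).

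| d (ng/mL) | calculation | share due to arm |
|---|---|---|
| 10 | 25 / (25 + 170.3) | 13% |
| 15 | 56.25 / (56.25 + 170.3) | 25% |
| 20 | 100 / (100 + 170.3) | 37% |

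On these assumptions, 63-87% of the variation that the correlation uses is not randomised.

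**False-positive rate with no true effect.** Simulated trials, 1:1, two-sided 5% level (assumed), 4,000 runs per scenario. One background factor has within-arm correlation r with 25(OH)D change and −r with periodontal change (lower = better). Neither arm nor 25(OH)D affects periodontal change. The value of r is assumed. So is n: 300 is the number of completers required in protocol section E.1, and 150 is half that, because the number of women examined is not stated.

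Percentage of trials in which the correlation test rejects:

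| n | d | r = 0 | r = 0.1 | r = 0.2 | r = 0.3 |
|---|---|---|---|---|---|
| 300 | 10 | 5.2 | 5.2 | 9.8 | 30.2 |
| 300 | 15 | 5.4 | 4.8 | 9.0 | 26.8 |
| 300 | 20 | 4.8 | 6.0 | 7.6 | 23.0 |
| 150 | 10 | 5.3 | 5.0 | 7.4 | 16.8 |
| 150 | 15 | 5.2 | 5.3 | 6.3 | 16.0 |
| 150 | 20 | 5.1 | 4.9 | 6.5 | 14.0 |

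A t-test by arm on the same data rejects in 4.3-5.5% of runs throughout. At n = 300, d = 15 and r = 0.4, the correlation test rejects in 69% and the by-arm test in about 5%.

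**Hand check of one cell** (n = 300, d = 15, r = 0.3). The spurious within-arm correlation is −r² = −0.09. Over both arms it is −0.09 × √(1 − 0.248) = −0.078. On the Fisher scale, 0.078 × √297 = 1.35, so the rejection probability is about P(Z > 1.96 − 1.35) = P(Z > 0.61) = 27%, in line with the simulated 26.8%.

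**The case against.** **The SAP already allows a by-arm comparison.** It does, in general terms. A reader might infer from D(17)(a) that the plan rules out comparing periodontal change by arm; the documents do not support that. What stands is narrower: no such comparison is specified for these measures, while a different analysis is.

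**The earlier trials show the size of the problem.** A reader might take the pooled result in protocol section C as a measure of how far the two analyses diverge. By arm, "No differences were noted between groups in terms of independent or combined comorbidities of pregnancy"; by achieved level, the OR was 0.84 per 10 ng/mL (95% CI 0.74-0.96, p = 0.0095). That reading goes too far. The pooled outcomes include no periodontal measure, no by-arm estimate or interval is given, and the OR is adjusted for race/ethnicity and study while no adjustment is stated for the arm comparison. Section C also reports a by-arm difference in combined comorbidities, controlling for race, in the trial with 400, 2000 and 4000 IU arms (p = 0.03). The pooled result shows only that the two analyses can disagree for comorbidities.

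**Confounders will be adjusted for.** The SAP plans adjustment in general, but D(17)(a) describes a plain correlation, and adjusting for measured factors does not restore what randomisation gives.

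**A status-response analysis has its place.** Agreed. The first objective asks how deficiency leads to imbalance, and the correlation is relevant to that. It does not answer the second objective.

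**This is only one case of a wider framing.** The primary outcome is also worded by vitamin D status, so the issue is broader. But rewording the primary outcome would leave the explicit rule in D(17)(a) in force.

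**The inflation is assumed.** True. With r = 0.1 there is almost none, and the documents give no value for r, d or the number of women examined.

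**Conclusion.** The point holds in limited form. For the major periodontal outcome, the plan specifies a correlation with a post-randomisation variable and leaves the available randomised comparison unspecified. An association in the beneficial direction could arise with no effect of supplementation.

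The size for periodontal measures cannot be taken from the documents. Under the stated assumptions at n = 300, the false-positive rate of the correlation runs from about 5-6% (r = 0.1) to 23-30% (r = 0.3), against about 5% by arm. These figures illustrate the mechanism and do not predict this trial's result.

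The weight is modest. Periodontal change is major only within its own item; Study Design names it neither as a primary nor as a secondary outcome.

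**What to change.** In protocol D(17)(a) and in the SAP:

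- Make the main periodontal analysis a comparison of the 28- and 36-week measures between the 400 and 4400 IU arms as randomised, using a mixed model or ANCOVA with baseline periodontal value and ethnicity.
- Include all women with a baseline and at least one follow-up examination. For the analysis, keep women given open-label vitamin D in their assigned arm.
- Keep the correlation with change in 25(OH)D as an exploratory analysis, labelled observational.
- Report the number of women examined per arm at each time point.

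The cost is wording in two documents; the examinations and 25(OH)D assays are already planned. There is a small downside. The examination is optional, so the by-arm estimate may be imprecise. Open-label use dilutes the contrast: for women enrolled at 10-14 weeks, 3 months (about 13 weeks) later is about 23-27 weeks, before both follow-up examinations.

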1. RISKS TO THE SUBJECTS

This is a randomized, double-blind, placebo-controlled trial of vitamin D supplementation during pregnancy, funded by the Kellogg Foundation. [name] is the PI of the study. For the parent protocol, 300 women must complete the study (through delivery) for the necessary statistical power (100 Hispanic, 100 African-American, and 100 Caucasian); half of each ethnicity will be randomized to 400 IU vitamin D/day and half to 4400 IU vitamin D/day. These women will be between 18-45 years of age, in good general health; exclusion criteria will be: mothers with pre-existing parathyroid disease or uncontrolled thyroid disease, mothers with multiple fetuses, and mothers with sickle cell disease, sarcoidosis, Crohn's disease, or ulcerative colitis. There will be a subgroup of pregnant women (projected 100 total) of all ethnicities who will have known diseases such as diabetes, hypertension, HIV or a body mass index > 49; these women will also be randomized to either 400 IU vitamin D/day or 4400 IU vitamin D/day, but in a separate randomization scheme, not dependent on completed subjects yielding a statistical power difference.

The targeted/planned enrollment table allows for a 30% dropout rate; information for our two previous large randomized clinical trials of vitamin D and pregnancy supports this rate. The targeted/planned enrollment table does NOT include the subgroup of pregnant women of all ethnicities who will have known diseases.

| TARGETED/PLANNED ENROLLMENT: Number of Subjects | | | | |
|---|------------|-------|-------|--|
| | Sex/Gender | | | |
| Ethnic Category | Females | Males | Total | |
| Hispanic or Latino | 150 | 0 | 150 | |
| Not Hispanic or Latino | 300 | 0 | 300 | |
| Ethnic Category: Total of All Subjects* | 450 | | | |
| Racial Categories | | | | |
| American Indian/Alaska Native | 0 | 0 | 0 | |
| Asian | 5 | 0 | 5 | |
| Native Hawaiian or Other Pacific Islander | 0 | 0 | 0 | |
| Black or African American | 150 | 0 | 150 | |
| White | 295 | 0 | 295 | |
| Racial Categories: Total of All Subjects* | 450 | 0 | 450 | |

Targeted/Planned Enrollment Table

Total Planned Enrollment 450

*The "Ethnic Category: Total of All Subjects" must be equal to the"Racial Categories: Total of All Subjects".

Pregnant women, 18-45 years of age will be recruited, of Hispanic, African-American and Caucasian ethnicities (may have a few Asians; will not exclude American Indian and Native Hawaiian if they are interested). All subjects will be receiving their prenatal care in the Charleston, SC area. All women will be less than 14 weeks of gestation at enrollment. This is a vitamin D supplementation study in pregnant women; so therefore, all women must be pregnant. The research question to be addressed is relevant only to women (pregnancy). A blood sample from the child of the pregnant women will be collected at birth, and the child will have a visit (with mother) at around 18 months of age to examine the first 4 baby teeth that have erupted and also to obtain a sample of the child's blood at that age for measurement of vitamin D.

Activity #7 (Objective #3) will not consent any additional subjects, because we are requesting a waiver of consent and HIPAA for deidentified record review of women who delivered babies at MUSC since September 2015.

b. Sources of Materials

The sources of research material will be maternal interview, history and physicals at clinic visits, the questionnaires, the lab reports for blood and urine analyses, the dental periodontal exam results, the dental salivary occult blood results, the vaginal swab results, the placental pathology report, the medical records of each mother and her infant following delivery, and the photographic teeth results on the infants.

The material/data that is routinely found in a maternal health record during pregnancy (including information on past pregnancies and disease history) will be utilized in the study. There are additional materials and data from questionnaires, blood, urine, saliva, infant teeth, placental tissue and vaginal samples that will be obtained for research purposes only.

A master list will be stored with study files accessible for clinical intervention only. The PI and study staff will have access to the master list. All archived samples and samples provided to collaborating laboratories will be identified with study subject numbers only. The DNA samples collected will have no recontact.

c. Potential Risks

Potential Risks of Phlebotomy and Blood Removal: The total amount of blood to be drawn at each maternal visit is as follows: visits 1 and 4, 31.5 mL; visits 2 and 8 (delivery), 22.5 mL; visits 3, 5, and 6, 17.5 mL; and visit 7, 37.5 mL. The total amount of blood drawn over the study will not exceed 200 mL. The risks of maternal phlebotomy include a slight pain when the needle is inserted into the vein. Momentary discomfort may occur. Pressure will be applied to the arm following the procedure to minimize the risk of bruising. There is a slight chance of inflammation of the vein and/or blood clot formation, but this is extremely rare. Fainting could occur, but this is rare. The same risks apply to the blood draw for the child. Every attempt will be made to minimize discomfort, including application of a topical anesthetic (EMLA cream) to the child's arm prior to venipuncture. These procedures were in place for our two previous vitamin D supplementation trials during pregnancy (HR #10727 and HR #16476).

Potential Risks of Dental Procedures: The risks of the dental procedures include temporary discomfort associated with periodontal probing and temporary discomfort of a dry mouth after providing a saliva specimen. Because of the transient bacteremia with periodontal probing, the few women who are usually premedicated with antibiotics before routine dental treatments will be excluded from the periodontal probing.

Potential Risk of Obtaining Umbilical Cord Blood: The total amount of blood to be collected from the umbilical cord is 30 mL. Since this procedure will be performed after delivery, there is no risk to either the mother or the infant during this procedure.

Potential Risks of Vitamin D Supplementation: There is a possibility that the treatment (dose of vitamin D) that each subject receives may prove to be less effective or to have more side-effects than the other study treatment (other dose of vitamin D) or other available treatments. The risks of maternal high dose vitamin D supplementation are hypercalciuria and hypercalcemia. There is a small risk that the woman's blood calcium level would increase in response to higher dose vitamin D supplementation. In the more than 540 women in the two prior vitamin D pregnancy supplementation trials (5, 6) and in the more than 340 mothers and infants who participated in the recently completed vitamin D lactation supplementation trial conducted at MUSC and the University of Rochester, this has not happened previously at this dose. The dose of vitamin D (4400 IU/day) used in this study is just over the limits established by the Institute of Medicine in 2010 (3). The PI and co-investigator do have an IND from the FDA (IND 66,346) for the administration of this dose of vitamin D and a higher dose in pregnant and lactating women; this protocol has been added to the IND. If, after 3 months on vitamin D supplementation, a woman is still frankly vitamin D deficient (less than 15 ng/ml), she will receive open label vitamin D gummies as requested by the FDA (IND 66,346). In two previous large randomized controlled trials of vitamin D supplementation during pregnancy and one large randomized controlled trial of vitamin D

supplementation during lactation, there was no difference in serum calcium or urinary calcium/creatinine ratios between the treatment groups (please see attached papers).

Potential Risks to the Fetus: During pregnancy, the developing fetus' vitamin D levels are about 70% of maternal serum vitamin D levels (5, 6). In the more than 540 women who participated in our two previous vitamin D supplementation studies, there was no identified increased risk to the developing fetus as per our two Data Safety and Monitoring Committees. Yet, some unknown risk of high dose maternal vitamin D supplementation on the fetus could be possible. By monthly monitoring of maternal serum vitamin D levels, we will ensure that the fetal levels remain in the normal range.

Potential Risks of Vaginal Swabs: Vaginal swabs obtained by the subjects do not carry a risk greater than insertion of a tampon.

Potential Risk of Breach of Confidentiality: As with any research study, there is a small risk that medical information, laboratory reports and data could become available to individuals outside the study. Every effort will be made to ensure that this does not happen.

Potential of Unknown Risks: The experimental trial may have unknown side effects that previously have not been reported (unexpected and unanticipated adverse events or effects).

The only alternative to this treatment regimen with vitamin D is the standard prenatal vitamin prescription (with 400 IU vitamin D_3 per tablet) taken daily throughout pregnancy. This regimen may not be advantageous if a woman is deficient in vitamin D.

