4. IMPORTANCE OF THE KNOWLEDGE TO BE GAINED

The issue of maternal supplementation with vitamin D becomes relevant for thousands of women and their unborn fetuses due to recent public health information showing that the majority of pregnant women have inadequate vitamin D levels and decreased sunlight exposure. The potential co-morbidities of pregnancy caused by vitamin D insufficiency or deficiency are increasing and occur with more frequency in African-American and Hispanic ethnicities. As shown in our previous vitamin D supplementation pregnancy trials, hypovitaminosis D is a preventable disorder with adequate supplementation; we strongly believe that the DRI for pregnant women, especially darkly pigmented individuals is woefully inadequate. Optimal vitamin D supplementation becomes an issue for the majority of pregnant women in this country and is necessary to decrease health disparities due to ethnicity.

The results of our previous vitamin D supplementation clinical trials in pregnancy did not show any detrimental effects (hypercalcemia or hypercalciuria) of daily intake of 4000 IU of vitamin D (5, 6). While in the NICHD vitamin D supplementation trial, there was a trend toward reduction in co-morbidities of pregnancy (5), in the Thrasher Research Fund trial involving community-based women living at or near the poverty level, there was evidence of reduced preterm labor, preterm birth, and infection as a function of maternal total circulating 25(OH)D levels, effects that persisted even after controlling for race (6). Yet, in both studies where the health status of the mother was not the focus of the trial nor was immune function, these are post-hoc analyses and can only suggest correlation. In the present RCT, we hope to show statistical differences in the co-morbidities, and show improved immune function with improved vitamin D status.

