Changes in vitamin D outcomes will be compared between treatment arms with the additional information from sunlight exposure, pigmentation/melanin index, maternal physical activity assessment, maternal dietary history, health, and medication questionnaires. This detail will allow the separation of changes in vitamin D parameters as a function of confounding factors from supplementation. The study is powered to explore the degree to which changes in vitamin D parameters are a function of supplementation and ethnicity. To assess whether there are differences in the slopes or linear dissimilarities in the outcomes over time, repeated measures techniques will be used to compare longitudinal changes in outcomes between groups. This technique also provides a graphical depiction of the slopes over time and can identify if there are linear or plateau responses to differences in vitamin D supplementation concentration; it also will allow determination of data transformation techniques required for subsequent analyses if the slopes over time are non-linear.

The final step in the second statistical approach will determine whether potential group differences in the various outcomes are a function of any of the potential confounders—with particular attention to skin pigmentation and sunlight exposure. This step will identify changes in outcomes associated with population factors independent of the group (supplementation) assignment. The extent of more complex statistical analyses will be predicated on the number of individuals comprising specific strata, and thus, restricted by a reduction in the statistical power. Such comparisons will be reported as information for future studies. To clarify, using sunlight exposure as a representative example, the independent effect of vitamin D supplementation may be found to have been modified by the amount of sunlight exposure. As such, the changes in outcomes attributable to each factor, independently, and then when considered in combination will be partitioned. While the major goal of this study is to examine the various outcomes as an independent function of vitamin D supplementation—thereby controlling for all other group differences, the changes in outcomes that are associated with these group differences will be examined and reported in detail. In this way, the changes in vitamin D that are associated with each factor independently will be partitioned.

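### The claim that 300 completers give the necessary power holds for the SAP's 25(OH)D comparison but not for the protocol's health-status primary or comorbidity aim

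*Protocol*

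**What the plan says.** Protocol section E.1 (Risks to the Subjects) states that "300 women must complete the study (through delivery) for the necessary statistical power", made up of 100 women from each of three ethnic groups, and that "half of each ethnicity will be randomized to 400 IU vitamin D/day and half to 4400 IU vitamin D/day". On enrolment it adds: "The targeted/planned enrollment table allows for a 30% dropout rate"; the table totals 450.

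The documents describe what is to be shown in different ways:

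- Protocol section D, Study Design: "The primary outcome variable is maternal and neonatal health status as a function of maternal and infant vitamin D status".
- Protocol section E.4: "In the present RCT, we hope to show statistical differences in the co-morbidities".
- SAP, opening paragraph: the primary analysis compares maternal 25(OH)D between the two supplementation groups.
- SAP, second statistical approach: "The study is powered to explore the degree to which changes in vitamin D parameters are a function of supplementation and ethnicity".

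Protocol section D(8), Sample Size, reports that calculations were made. It gives no alpha, power, effect size, standard deviation or event rate, and it describes every outcome marker as a normally distributed quantity, which does not fit binary pregnancy complications.

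**The concern.** A reader of the protocol alone will apply the unqualified power statement to the outcome that the protocol calls primary. Section C strengthens that reading: it says that trials designed and powered for health outcomes have yet to be done, and E.4 then presents this trial as the one meant to go beyond earlier post-hoc findings.

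If power for the composite is in fact low, a null result by arm is likely even if the earlier association is wholly causal. It would come from a trial described as adequately powered, and could be taken as evidence of no effect. The same risk applies to a non-significant difference between ethnic groups, because the end of protocol section A already asserts that the benefit holds across race.

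**Working it through.** **Plan's own figure.** 300/(1 − 0.30) = 429, and 450 × 0.70 = 315, so 450 enrolled covers 300 completers. The 300 itself cannot be reproduced, because no design inputs are given. Two-sided alpha of 0.05 is assumed throughout. The SAP mentions Bonferroni adjustment without giving the number of comparisons; any division of alpha lowers the power figures below.

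**25(OH)D by arm (SAP primary).** Section C gives SDs of change of 13.2 and 12.9 ng/mL, taken as 13. The difference detectable with 80% power is 2.80 × SD × √(2/n per arm).

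- Overall, 150 per arm: 2.80 × 13 × √(2/150) = 4.2 ng/mL.
- Within one ethnic group, 50 per arm: 2.80 × 13 × √(2/50) = 7.3 ng/mL.
- Number per arm needed for 10 ng/mL: 2 × (2.80 × 13/10)² ≈ 26.5, or about 27. Power for 10 ng/mL with 150 per arm exceeds 99%.

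**Combined comorbidities by vitamin D status (the wording of section D).** Section C gives an odds ratio of 0.84 per 10 ng/mL (95% CI 0.74-0.96, p=0.0095). The dose groups sum to 110 + 197 + 189 = 496 women.

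- p=0.0095 corresponds to z = 2.594.
- Scaled to 300 women: 2.594 × √(300/496) = 2.017.
- Power = Φ(2.017 − 1.960) ≈ 52%. If all 450 women contributed, it would be about 70%.

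This treats the earlier estimate as true, and assumes the same spread of 25(OH)D and the same event rate as in the earlier cohort.

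**Combined comorbidities by arm.** The arm odds ratio is 0.84^(separation/10), applied to a control rate p₁ to give p₂. Power = Φ{[|p₁ − p₂| − 1.96√(2p̄(1−p̄)/n)] / √[(p₁(1−p₁) + p₂(1−p₂))/n]}, with n = 150. Separation and control rate are assumptions; the documents give neither.

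Example: separation 15 ng/mL, control rate 40%. Odds ratio 0.84^1.5 = 0.77, so p₂ = 33.9% and power = Φ[(0.061 − 0.109)/0.0556] ≈ 19%.

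| Separation (ng/mL) | Arm odds ratio | Control 10% | Control 40% | Control 60% |
|---|---|---|---|---|
| 10 | 0.84 | 6% | 11% | 11% |
| 15 | 0.77 | 9% | 19% | 20% |
| 20 | 0.71 | 13% | 30% | 32% |
| 25 | 0.65 | 18% | 43% | 46% |

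**Other associations in section C, by arm, 15 ng/mL separation, 150 per arm.**

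- Preterm birth, 0.50 per 10 ng/mL (arm odds ratio 0.354): 57%, 74% and 84% at control rates of 10%, 15% and 20%.
- Preterm labor or birth, 0.72 per 10 ng/mL (arm odds ratio 0.611): 21% at a control rate of 10%, rising to 56% at 50%.
- Preterm birth without preeclampsia in the combined cohort, 0.83 per 10 ng/mL: 10-15% at control rates of 10-20%.

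**Difference in 25(OH)D response between two ethnic groups.** Detectable difference = 2.80 × 13 × √(4/50) = 10.3 ng/mL, which is 10.3/15.2 = 68% of the mean rise on 4000 IU reported in section C. Power is about 27% for a 5 ng/mL difference and 78% for 10 ng/mL.

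**The case against.** The strongest reply is that E.1 names no endpoint. The sample-size section speaks of normally distributed markers, the SAP's primary analysis is 25(OH)D, and the SAP's only power sentence concerns vitamin D parameters. Read that way, E.1 is correct, and the sentence in E.4 is a hope and not a power claim. This stands as far as 25(OH)D goes. It does not rescue an unqualified statement in a protocol whose named primary outcome is health status.

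A reader might infer more than the documents support in five ways.

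- *That 300 is too few for every health outcome.* Section C also reports an odds ratio of 0.50 for preterm birth, which gives 57-84% under the assumptions above, and p=0.03 across three dose groups for combined comorbidities in one earlier trial.
- *That the by-arm range comes from the protocol's own figures.* Only the odds ratio does.
- *That the earlier combined result contradicts the power claim.* Section C says of the dose groups that "No differences were noted between groups in terms of independent or combined comorbidities of pregnancy", and 110 v 189 women carry nearly the precision of 150 v 150 (1/110 + 1/189 = 0.0144; 2/150 = 0.0133). But all the 400 IU controls came from one trial while the 4000 IU women came from both, and the groups differed in parity, insurance and education. The contrast is partly non-randomised, and a null result does not refute a power statement.
- *That ethnic differences cannot be resolved.* The SAP claims power only to explore. Differences of about 10 ng/mL are detectable, and the planned covariate and repeated-measures models could lower that figure.
- *That 300 was derived from 25(OH)D.* No derivation is given. The calculation shows only that 300 is ample for it.

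**Conclusion.** The concern holds in a limited form. The power statement is true for 25(OH)D by arm and untrue, as an unqualified claim, for the comorbidity composite. At the association in section C, power for the composite is about 52% when analysed by vitamin D status and about 6-46% by arm.

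The 52% rests on the earlier estimate and the earlier spread of 25(OH)D. With no 2000 IU arm here, the spread could be wider and power higher. The by-arm range rests on assumed control rates of 10-60% and separations of 10-25 ng/mL. Two features of the protocol could narrow the separation and lower power: open-label vitamin D for women below 15 ng/mL after three months, and clinic-wide supplementation towards 40 ng/mL from September 2015. The documents quantify neither. Every composite scenario examined at the 0.84 odds ratio with 300 completers falls well short of 80%.

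**What to change.** - **Protocol E.1:** limit the power statement to 25(OH)D by arm and give the detectable differences (about 4.2 ng/mL overall and 7.3 within an ethnic group, at SD 13). Say that 300 is ample for this comparison; do not say it was derived from it unless the original calculation can be produced.
- **Protocol E.1 and E.4:** state that power for the comorbidity composite is well below 80% at the association in section C, and show the assumed control rates and separations.
- **SAP, second statistical approach:** state that differences in response between ethnic groups below about 10 ng/mL (SD 13, before any gain from covariates or repeated measures) are exploratory.
- **Protocol section D and SAP opening paragraph:** agree on which outcome is primary.
- **Reporting:** give health outcomes and ethnicity interactions as estimates with confidence intervals, and do not report non-significance as absence of effect.

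The cost is wording in both documents and a less favourable stated power. No additional participants are needed.
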